#### 4.2 Definition of Dose-Limiting Toxicity

Dose limiting toxicity (DLT) will be defined as the occurrence of any of the following during the first cycle of protocol treatment:

- Hematologic: Defined as neutropenia (ANC  $< 500/\text{mm}^3$ ) or thrombocytopenia (platelets  $< 25,000/\text{mm}^3$ ) lasting longer than seven days.
- Non-hematologic: Defined as any Grade 3 pomalidomide-related toxicity lasting seven days or longer or Grade 4 toxicity. Nausea, vomiting, and diarrhea are not DLTs if they can be managed with standard antiemetic and antidiarrheal medications. Incidental laboratory abnormalities that do not reflect underlying organ dysfunction are not DLTs.
  - Any instance of bullous erythema multiforme syndrome, toxic epidermal necrolysis syndrome (TENS), or Stevens-Johnson syndrome
- Failure to complete  $\geq 80\%$  of the planned 21 doses (i.e.,  $\geq 17$  doses) of a pomalidomide treatment course due to pomalidomide-related toxicities.

Toxicities will be graded according to the NCI Common Terminology Criteria for Adverse

Events (CTCAE) Version 5.0 as outlined in [Section 6.0](#). If multiple toxicities are seen, the presence of DLT will be based on the most severe toxicity experiences.

During the period for evaluating dose-limiting toxicity, participants who withdraw from the study or do not complete the required cycles of treatment owing to reasons other than drug-related adverse events can be replaced.

See [Section 10.1.2](#) for early stopping rules based on the frequency of first-cycle DLT.

#### **4.3 General Concomitant Medication and Supportive Care Guidelines**

In general, concomitant medications and therapies deemed necessary for the supportive care and safety of the participant, including transfusions of blood and blood products, antibiotics, and antiemetics when appropriate, are allowed.

The administration of any other therapies intended to treat KS including chemotherapy and biologic agents is **NOT** permitted. The use of other concurrent investigational drugs is not allowed.

All participants must be on stable antiretroviral therapy (ART) for a minimum of 12 weeks prior to study entry with an acceptable regimen that adheres to national guidelines for treatment of HIV infection. Participants are **not allowed** to receive zidovudine (AZT; ZDV) as part of the ART regimen, since it is myelosuppressive. Zidovudine may be discontinued and substituted as clinically indicated upon enrollment. If zidovudine is substituted, it must be at least 7 days prior to therapy initiation (see [Section 3.2.5](#)).

Strong inhibitors of CYP1A2, including: amiodarone, cimetidine, fluoroquinolones (e.g., ciprofloxacin, enoxacin), fluvoxamine; and ticlopidine are prohibited.

Co-administration of efavirenz, an inhibitor of CYP1A2, with strong inhibitors of CYP3A4 and P-glycoprotein (P-gp) is prohibited.

Use of erythropoietin is prohibited.

Because there is a potential for interaction of pomalidomide with other concomitantly administered drugs through the cytochrome P450 system, the case report form must capture the concurrent use of all other drugs, over-the-counter medications, or alternative therapies. The protocol chairs should be alerted if the participant is taking any agent known to affect or with the potential to affect selected CYP450 isoenzymes. [Appendix VI](#) presents guidelines for identifying medications/substances that could potentially interact with the study agent.

Participants MUST receive medically appropriate care and treatment for HIV infection, including antiretroviral medications. Due to known cytochrome P450 inhibitory effects of protease inhibitors, particularly for ritonavir, the case report form will particularly note the use of ritonavir for HIV management.

##### *Anticoagulation consideration*

Pomalidomide increases the risk of thrombotic events in patients who are at high risk or with a history a thrombosis, in particular when combined with other drugs known to cause thrombosis.

Participants must receive aspirin by mouth daily x 28 days for each cycle of pomalidomide

and for 30 days after the last pomalidomide dose. The recommended dose is 75-100mg daily, unless they are already receiving aspirin at an equal or higher daily dose for another indication. If the recommended dose of aspirin is not available, a dose of up to 325 mg daily may be administered.

#### *Steroid considerations*

Concurrent administration of corticosteroids greater than doses required for treatment of adrenal insufficiency is prohibited.

#### *Estrogen-containing compounds*

Concurrent administration of estrogen containing compounds, including estrogen containing contraceptives, may increase the risk of thrombosis. These compounds should be avoided during pomalidomide treatment.

#### *Tobacco use*

Concurrent tobacco use during pomalidomide therapy may increase the risk for thrombosis. Study staff will obtain information on participants' tobacco smoking history with participants at baseline. Participants who are current smokers will be provided guidance for smoking cessation per local policies.

#### *Management of concurrent infections*

The management of active tuberculosis (TB) or cryptococcal meningitis (CM) for participants will be per the local standard of care at the respective sites where the study is being carried out.

### **4.4 Duration of Therapy**

Treatment may continue for up to 6 cycles for participants with stable disease, or up to 12 cycles if they have complete or partial response, or until one of the following criteria applies:

- Disease progression
- Intercurrent illness that prevents further administration of treatment
- Unacceptable adverse event(s), as defined in [Section 5.1](#)
- Participant decides to withdraw from the study
- General or specific changes in the participant's condition render the participant unsuitable for further treatment in the judgment of the investigator, including but not limited to:
  - Pregnancy
  - Failure to return for scheduled follow up for more than 42 days

### **4.5 Duration of Follow Up**

Participants with complete response (CR) or partial response (PR) will be followed for up to 48 weeks after their last dose of study treatment or until PD or death, whichever occurs first, for safety and response duration ([Section 8.4](#)). Participants with stable disease (SD) or progressive disease (PD) will be followed for 30 days after treatment discontinuation.

Participants removed from study treatment for unacceptable adverse event(s) will be followed at least weekly until resolution or stabilization of the adverse event, after which they will be followed according to their response status.

#### **4.6 Criteria for Removal from Treatment**

Participants will be removed from study treatment when any of the criteria listed in [Section 4.4](#) applies. The reason for study treatment removal and the date the participant was removed must be documented in the Off Protocol Treatment Form in Advantage eClinical.

## 5.0 DOSING DELAYS/DOSE MODIFICATIONS

### 5.1 Dose Modifications for Pomalidomide

#### 5.1.1 Dose reduction steps

**Table 5-1. Pomalidomide Dose Reduction Steps**

Dose Level	Dose and Schedule
Dose level 1 (starting dose)	4 mg daily on Days 1-21 every 28 days
Dose level -1	3 mg daily on Days 1-21 every 28 days

#### 5.1.2 Instructions for initiation of a new cycle

A new course of treatment may begin on the scheduled day 1 of a new cycle if:

- The ANC is  $\geq 1,000$  cells/mm^3 ( $1.0 \times 10^9$ /L); The platelet count is  $\geq 50,000$  cells/mm^3 ( $50.0 \times 10^9$ /L);
- Any drug-related rash or neuropathy that may have occurred has resolved to  $\leq$  Grade 1 severity;
- Any other drug related adverse events that may have occurred have resolved to  $\leq$  Grade 2 severity.

If these conditions are not met on day 1 of a new cycle, the participant will be evaluated weekly and a new cycle of treatment will not be initiated until the toxicity has resolved as described above. If pomalidomide dosing was halted during the previous cycle and was restarted with a one-level dose reduction without requiring an interruption for the remainder of the cycle, then that reduced dose level will be initiated on day 1 of the new cycle.

Unless otherwise specified in this section, if any Grade 3 or 4 toxicity persists for longer than two weeks after withholding pomalidomide, pomalidomide will be stopped permanently.

#### 5.1.3 Instructions for dose modifications or interruption during a cycle

**Note: If the site investigator has compelling evidence that the toxicity is NOT related to the study drugs or is not clinically significant (e.g., alopecia, electrolyte abnormalities that can be corrected with supplementation), then management of drug dosing is at the discretion of the site investigator after consultation with the study chair(s). Table 5-2. Dose Modifications For Non-Hematologic Toxicity**

Toxicity	Dose Modification
Rash = Grade 3	Hold dose for remainder of cycle. Decrease by one dose level when dosing restarted at next cycle (rash must resolve to $\leq$ Grade 1).

Toxicity	Dose Modification
Rash = Grade 4 or bullous dermatitis (any grade)	Discontinue participant from pomalidomide treatment regimen.
Stevens-Johnson Syndrome (any Grade)	Discontinue participant from pomalidomide treatment regimen.
Anaphylaxis (any Grade)	Discontinue participant from pomalidomide treatment regimen.
Constipation $\geq$ Grade 3	Hold dose for remainder of cycle. Initiate bowel regimen. Decrease by one dose level when dosing restarted at next cycle (constipation must resolve to $\leq$ Grade 2).
Thromboembolism event $\geq$ Grade 3	Hold dose for remainder of cycle. Initiate anticoagulation treatment. Maintain dose level when dosing restarted at next cycle at discretion of treating physician.
Hypo/hyperthyroidism $\geq$ Grade 2	Hold dose for remainder of cycle. Initiate appropriate medical therapy. Maintain dose level when dosing restarted at next cycle at discretion of treating physician.
Peripheral neuropathy = Grade 3	Hold dose for remainder of cycle. Decrease by one dose level when dosing restarted at next cycle (neuropathy must resolve to $\leq$ Grade 1).
Peripheral neuropathy = Grade 4	Discontinue participant from pomalidomide treatment regimen.
Other <math>\geq</math> Grade 3 pomalidomide-related adverse events	Hold dose for remainder of cycle. Decrease by one dose level when dosing restarted at next cycle (adverse event must resolve to $\leq$ Grade 2).

### **Dose modifications for non-hematologic toxicity**

#### **Grade 3 rash or peripheral neuropathy**

If a participant experiences a new Grade 3 rash or peripheral neuropathy, pomalidomide must be withheld until the toxicity has resolved to  $\leq$  Grade 1. If the participant is receiving 4 mg/day, the daily dose should be reduced by one dose level, to dose level -1 (3 mg/day). If Grade 3 toxicity recurs in a participant receiving 3 mg/day, pomalidomide treatment will be stopped.

If any participant experiences Steven-Johnson Syndrome, anaphylaxis, or Grade 4 peripheral neuropathy, pomalidomide must be discontinued.

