### All other Grade 3/4 non-hematologic toxicities

If a participant experiences Grade 3/4 non-hematologic toxicity, pomalidomide must be withheld until the toxicity has resolved to  $\leq$  Grade 2. Participants receiving 4 mg/day may then have treatment resumed at dose level -1 (3 mg/day). If the Grade 3/4 toxicity occurs or recurs at dose level -1, pomalidomide treatment will be stopped.

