#### Grade 3/4 thrombocytopenia

If the participant experiences Grade 3 or 4 thrombocytopenia (platelet count decrease), defined as a platelet count  $< 50 \times 10^9/L$ , pomalidomide must be withheld until the toxicity has resolved to  $\leq$  Grade 2. Participants receiving 4 mg/day may then have treatment resumed at dose level -1 (3 mg/day). If Grade 3 or 4 thrombocytopenia occurs or recurs at dose level -1, pomalidomide treatment will be stopped permanently. If, at any time, Grade 3 or 4 thrombocytopenia persists for longer than two weeks after withholding pomalidomide, pomalidomide will be stopped permanently.

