#### Grade 3/4 neutropenia (see [Figure 5-1](#))

If a participant experiences Grade 3 or 4 neutropenia (absolute neutrophil count decrease), defined as a calculated ANC  $< 1.0 \times 10^9/L$ , treatment with pomalidomide must be withheld. If available, growth factor (filgrastim or pegfilgrastim) may be started at standard doses (see Manual of Procedures (MOP) for acceptable dosing regimens). NOTE: Growth factors will not be provided by the study. If the ANC returns to  $\leq$  Grade 2 within 1 week without any additional toxicity (i.e., fever), treatment with pomalidomide may continue without dose modification with continued growth factor support in all subsequent treatment cycles. In participants receiving growth factor support, if the ANC fails to return to  $\leq$  Grade 2 within one week, or if additional toxicity is seen (i.e., fever), or if  $\geq$  Grade 3 neutropenia recurs in a participant on pomalidomide with growth factor support, participants receiving 4 mg/day may then have treatment resumed at dose level -1 (3 mg/day). If the Grade 3 or 4 neutropenia occurs or recurs at dose level -1, pomalidomide treatment will be stopped.

If growth factors are not available or cannot be provided on a sustained basis for all subsequent treatment cycles, pomalidomide must be withheld until the toxicity has resolved to  $\leq$  Grade 2. Participants receiving 4 mg/day may then have treatment resumed at dose level -1 (3 mg/day). If the Grade 3 or 4 neutropenia occurs or recurs at dose level -1, pomalidomide treatment will be stopped permanently.

[figure not shown]
If, at any time, Grade 3 or 4 neutropenia persists for longer than two weeks after

withholding pomalidomide, pomalidomide will be stopped permanently.

*Grade 1-4 anemia*

No dose reductions will be performed for Grade 1-4 anemia. Participants who develop anemia may be transfused at the discretion of the investigator.

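### For a first Grade 3 rash or peripheral neuropathy that resolves in a participant on 3 mg/day, the Section 5.1 narrative and Table 5-2 conflict on what happens next

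*Combined protocol and SAP*

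**What the plan says.** Section 5.1 has two dose levels. Table 5-1 starts at 4 mg and ends at dose level -1, "3 mg daily on Days 1-21 every 28 days".

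For a new Grade 3 rash or peripheral neuropathy, the narrative in Section 5.1.3 orders a hold until Grade 1 or less and sends a participant on 4 mg/day to 3 mg/day. For a participant on 3 mg/day it adds only "If Grade 3 toxicity recurs in a participant receiving 3 mg/day, pomalidomide treatment will be stopped".

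Table 5-2 covers the same events without reference to the current dose. For Grade 3 neuropathy, after a hold for the rest of the cycle: "Decrease by one dose level when dosing restarted at next cycle (neuropathy must resolve to" Grade 1 or less). The Grade 3 rash row is built the same way.

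Section 5.1.2 lets a new cycle begin under conditions that include: "Any drug-related rash or neuropathy that may have occurred has resolved to" Grade 1 or less. It also has a general rule for Grade 3 or 4 events that do not settle: if the "toxicity persists for longer than two weeks after withholding pomalidomide, pomalidomide will be stopped permanently".

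The neighbouring rules are worded differently. For all other Grade 3/4 non-hematologic toxicities: if the "toxicity occurs or recurs at dose level -1, pomalidomide treatment will be stopped". For platelets: "If Grade 3 or 4 thrombocytopenia occurs or recurs at dose level -1, pomalidomide treatment will be stopped permanently". The neutropenia rule uses the same *occurs or recurs* form at dose level -1.

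**The concern.** The rash and neuropathy paragraph is the only one in Section 5.1.3 whose stop at 3 mg/day depends on *recurs* alone. A first event at that dose falls between a narrative that seems to permit resumption and a table that requires a reduction the protocol cannot supply.

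Taken literally, a first Grade 3 neuropathy at 3 mg is handled more leniently than a first Grade 3 constipation at 3 mg, which the narrative stops. Yet rash and neuropathy carry the stricter recovery threshold, Grade 1 rather than Grade 2.

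What is at stake is participant safety and uniform conduct across sites. One site could re-expose a participant to the same dose after Grade 3 neuropathy, while another permanently stops someone who may be responding.

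**Working it through.** No sample size, power or error rate is involved, so the check is a reading of the rules case by case.

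1. **4 mg/day, first event, resolves to Grade 1 or less.** Narrative: reduce to 3 mg. Table 5-2: reduce one level. The two agree.
2. **3 mg/day, repeat of the same Grade 3 event.** Narrative: stop. This is clear, although Table 5-2 still orders a decrease.
3. **3 mg/day, first event, still Grade 3 or 4 more than two weeks into the hold.** Section 5.1.2: permanent stop. Defined.
4. **3 mg/day, first event, resolves to Grade 1 or less.**
   - Narrative: the hold ends. A next dose is given only for 4 mg, and the stop applies only to recurrence.
   - Section 5.1.2: a new cycle may begin, with no dose stated for this case. Its carry-forward sentence covers only a participant already restarted one level lower.
   - Table 5-2: restart one level lower. Table 5-1: no such level.
   - The *occurs or recurs* stop for non-hematologic toxicity sits under a heading for all other toxicities, so it does not reach rash or neuropathy.

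Only case 4 lacks a consistent instruction. The narrative with Section 5.1.2 suggests 3 mg again, while Table 5-2 rules out the same dose and offers nothing that exists in its place.

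**Who could be in case 4?** Chiefly a participant reduced to 3 mg after a different Grade 3/4 event. Neutropenia is the likeliest. Section 2.2.1 reports Grade 3 or 4 neutropenia, given as an adverse event in 12 patients, among the first 22 in the earlier KS trial, and Section 5.1.3 reduces the dose when growth factor is unavailable or fails. That trial used 5 mg, and growth factor may keep some participants at 4 mg, so 12 of 22 shows that the route is plausible but does not estimate how many will take it.

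**How often would the event follow?** The documents do not say. Section 2.2.1 names no Grade 3/4 rash or neuropathy in those 22 patients and describes rash as mild, but its list may be incomplete.

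**The case against.** A reader might infer that Section 5.1 leaves no step at all that can be carried out. The documents do not support that. A hold that lasts until Grade 1, joined to a new-cycle condition set at Grade 1, implies a restart, and the dose in force is 3 mg. The defect is a conflict with Table 5-2 and the absence of an explicit choice.

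The phrase about Grade 3 toxicity recurring could also mean any second Grade 3 toxicity. Someone reduced for Grade 3 neutropenia would then stop at a first Grade 3 rash. That reading is available but not stated, and it fits poorly if the earlier event was Grade 4.

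A reader might also point to participants on 3 mg with no earlier Grade 3 event. Those routes are weak. The Grade 2 de-escalation in Section 2.3 is a design summary with no matching rule in Section 5.1. The lowered starting dose in Section 4.1.2 uses the same counts (Table 4-1) as the stop in Table 10-1. By the summary of changes, the last participant had to start by 1 December 2023, before version 10.0 was dated.

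Finally, a restart at 3 mg could be intended. The protocol does not reduce the dose after every serious event: Table 5-2 allows the level to be kept after thromboembolism, and after neutropenia "treatment with pomalidomide may continue without dose modification with continued growth factor support in all subsequent treatment cycles" under stated conditions. This is fair, and it is why the sponsor must be free to choose. But where Table 5-2 means the dose to be kept it says so, and for rash and neuropathy it orders a decrease. Continuous review of dose reductions by the protocol team (Section 4.1.2) would lessen differences between sites without removing them.

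**Conclusion.** The inconsistency is real and minor. It is confined to a first Grade 3 rash or peripheral neuropathy, in a participant on 3 mg/day, that resolves to Grade 1 or less. The mismatch in wording is certain. Which outcome the sponsor intended is not, although stopping is the only one that fits both the parallel rules and Table 5-2's refusal to restart at the same dose.

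Few participants are likely to be affected. That is a judgment, since no rate of these events at 3 mg is given. A reader might infer an effect on the response rate or its test; nothing in the documents supports one, and none is claimed. With enrolment due to close by the end of 2023 (Section 10.1.2), the benefit falls mainly to participants still within their 6 or 12 cycles.

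**What to change.** 1. In the rash and neuropathy paragraph of Section 5.1.3, replace the sentence on recurrence with one such as: *A Grade 3 rash or peripheral neuropathy that occurs or recurs at 3 mg/day ends pomalidomide treatment.*
2. In the four Table 5-2 rows that order a one-level decrease (Grade 3 rash, Grade 3 or higher constipation, Grade 3 neuropathy, other Grade 3 or higher related events), split the instruction: from 4 mg/day, restart at 3 mg/day; from 3 mg/day, discontinue. Keep the recovery grades. For constipation and the *other* row this only brings the table into line with the narrative.
3. If the sponsor intends a restart at 3 mg after a first rash or neuropathy, state that in both places instead.

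The main cost is clinical: under the stop rule, a possible responder whose first event at 3 mg has resolved would lose treatment. Administratively, Section 12.3 requires a written amendment approved by CTEP, the Investigator and each site's IRB/IEC, with national approval where applicable. It is best bundled with another amendment. No extra participants, visits or analyses are needed.

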### All other Grade 3/4 non-hematologic toxicities

If a participant experiences Grade 3/4 non-hematologic toxicity, pomalidomide must be withheld until the toxicity has resolved to  $\leq$  Grade 2. Participants receiving 4 mg/day may then have treatment resumed at dose level -1 (3 mg/day). If the Grade 3/4 toxicity occurs or recurs at dose level -1, pomalidomide treatment will be stopped.

### Dose modifications for hematologic toxicity

#### Grade 1/2

There will be no dose interruptions or reductions for Grade 1 or 2 hematological toxicity.

#### Grade 3/4 thrombocytopenia

If the participant experiences Grade 3 or 4 thrombocytopenia (platelet count decrease), defined as a platelet count  $< 50 \times 10^9/L$ , pomalidomide must be withheld until the toxicity has resolved to  $\leq$  Grade 2. Participants receiving 4 mg/day may then have treatment resumed at dose level -1 (3 mg/day). If Grade 3 or 4 thrombocytopenia occurs or recurs at dose level -1, pomalidomide treatment will be stopped permanently. If, at any time, Grade 3 or 4 thrombocytopenia persists for longer than two weeks after withholding pomalidomide, pomalidomide will be stopped permanently.

#### Grade 3/4 neutropenia (see [Figure 5-1](#))

If a participant experiences Grade 3 or 4 neutropenia (absolute neutrophil count decrease), defined as a calculated ANC  $< 1.0 \times 10^9/L$ , treatment with pomalidomide must be withheld. If available, growth factor (filgrastim or pegfilgrastim) may be started at standard doses (see Manual of Procedures (MOP) for acceptable dosing regimens). NOTE: Growth factors will not be provided by the study. If the ANC returns to  $\leq$  Grade 2 within 1 week without any additional toxicity (i.e., fever), treatment with pomalidomide may continue without dose modification with continued growth factor support in all subsequent treatment cycles. In participants receiving growth factor support, if the ANC fails to return to  $\leq$  Grade 2 within one week, or if additional toxicity is seen (i.e., fever), or if  $\geq$  Grade 3 neutropenia recurs in a participant on pomalidomide with growth factor support, participants receiving 4 mg/day may then have treatment resumed at dose level -1 (3 mg/day). If the Grade 3 or 4 neutropenia occurs or recurs at dose level -1, pomalidomide treatment will be stopped.

If growth factors are not available or cannot be provided on a sustained basis for all subsequent treatment cycles, pomalidomide must be withheld until the toxicity has resolved to  $\leq$  Grade 2. Participants receiving 4 mg/day may then have treatment resumed at dose level -1 (3 mg/day). If the Grade 3 or 4 neutropenia occurs or recurs at dose level -1, pomalidomide treatment will be stopped permanently.

[figure not shown]
If, at any time, Grade 3 or 4 neutropenia persists for longer than two weeks after

withholding pomalidomide, pomalidomide will be stopped permanently.

*Grade 1-4 anemia*

No dose reductions will be performed for Grade 1-4 anemia. Participants who develop anemia may be transfused at the discretion of the investigator.

